1.27 Special Concerns for the Use of Raltegravir in the Neonate

UGT1A1, the enzyme primarily responsible for raltegravir metabolism, is also the only enzyme that contributes to bilirubin glucuronidation in human hepatocytes, and as such is essential for the biliary elimination of bilirubin from the body [48]. Glucuronidation activity is low in fetuses and in the newborn immediately after birth but increases exponentially over the first weeks and months of life. Hepatic UGT activity in liver samples is very low in samples from 2nd trimester fetuses, and increases roughly 10 fold during the 3rd trimester and then another 100-fold during the first 3 months following a full term delivery [49]. The low level of hepatic UGT activity at birth plays a major role in the elevations of bilirubin routinely seen in the newborn, referred to as physiologic jaundice.

In adults, decreased UGT1A1 activity has been shown to result in increased plasma concentrations of both bilirubin and raltegravir. Atazanavir, an HIV protease inhibitor, is also an inhibitor of UGT1A1 and elevation of direct bilirubin is a very common side effect of atazanavir use in HIV infected adults. When raltegravir and atazanavir are co-administered, raltegravir AUC increases on average by 41% and C_{max} by 77% [50]. Similarly, the *UGT1A1* *28/*28 genotype, one of the common genotypes found in individuals with Gilbert's Syndrome, is characterized by a roughly 30% decrease in UGT1A1 activity and increased serum bilirubin concentrations [51, 52]. Following standard dosing with raltegravir, individuals with the *UGT1A1* *28/*28 genotype have on average an increase of 40% in raltegravir AUC and C_{max} and of 90% in trough concentration compared to individuals with wild type *UGT1A1*. Raltegravir elimination $t_{1/2}$ was not prolonged in the *UGT1A1* *28/*28 individuals, suggesting that increased raltegravir bioavailability due to decreased hepatic first pass metabolism may play a major role in the increase in raltegravir plasma concentrations seen in these individuals [53].

Administration of an exogenous drug that is eliminated by glucuronidation poses special risks in the newborn. Low UGT activity that results in decreased elimination of endogenous bilirubin and physiologic jaundice will also result in decreased metabolism

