To assess the safety and tolerability of RAL through 24 weeks of life, descriptive statistics will be calculated summarizing the proportion of infants who had an adverse event of Grade 3 or 4 severity or death based on safety data from study entry through 24 weeks of age on all safety evaluable infants in each of the four study groups. A similar analysis will be done to summarize proportion of infants who had an SADR of Grade 3 or 4 severity or death.

To investigate the relationship between neonatal raltegravir elimination and UGT1A-1 genotype, participants will be divided into subgroups, based on whether or not they exhibit polymorphisms on UGT1A-1. Descriptive analyses will be performed to compare these subgroups with respect to measures of central tendency and dispersion for raltegravir AUC.

Similar descriptive analyses will also be performed to investigate the association of UGT1A1 (*28/*28) and SLCO1B3 (rs2117032-C/T) with hyperbilirubinemia. If the sample size and the data distributions make this possible, a logistic regression model predicting for probability of neonatal hyperbilirubinemia with UGT1A1 (*28/*28) genotype, SLCO1B3 (rs2117032-C/T) genotype, gestational age and gender as predictors will be fitted on the pooled data across the two cohorts. Note that the sample size may be too small and/or there may be insufficient cases of hyperbilirubinemia to make this possible. If this analysis can be done, it will have minimal power, but the size and directionality of effects will be compared with those predicted on the basis of previous findings.

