4.9 Genotype Analysis

Purpose:

To list the tables for investigating the relationship between neonatal RAL elimination (as reflected in CL/F) and UGT1A-1 genotype, and the relationship between UGT1A-1 and SLCO1B3 with hyperbilirubinemia.

Analysis Program Validation:

Code review required.

Data:

HUMGENO table and LBW0093 CRF (TBILCV, BILPHOTO, BILTRANS, BILOTH and BILOTHSP).

Analysis:

- a) Response variables for genotype analysis:
 - UGT1A-1 genotype (presence or absence of *28/*28 genetic variant):
Wild-type: (TA)₆(TA)₆; mutation: (TA)₅(TA)₆, (TA)₆(TA)₇ and (TA)₇(TA)₇
 - SLCO1B3 (rs2117032-C/T) genotype:
C/C, C/T and T/T
 - Hyperbilirubinemia defined as total bilirubin exceeding 16.0 mg/dL or infant requiring exchange transfusion for hyperbilirubinemia

b) Output tables:

Table: Summary descriptive statistics (N, geometric mean, median, 25th and 75th percentiles, min, and max) on CL/F will be generated for the subgroups of participants depending on whether they exhibit the UGT1A1 polymorphism.

Table 8: Summary of Infant RAL CL/F between UGT1A1 Genotype Groups for Cohort 1 (mock-up table)

		UGT1A1 Genotypes					Overall	p-value ^a for all genotypes	p-value ^b for wild-type vs. mutation
		Wild-type	Mutation			Overall			
		(TA)6(TA)6	(TA)5(TA)6	(TA)6(TA)7	(TA)7(TA)7				
CL/F of RAL-naïve Infants	N								
	mean								
	median								
	...								
CL/F of RAL-Exposed Infants	N								
	mean								
	median								
	...								
CL/F of All Infants	N								
	mean								
	median								
	...								

a Comparison of median among different genotypes will use Kruskal–Wallis test for CL/F of all infants only. The formal comparison will be done only if we have enough infants in the listed genotype groups.

b Comparison of median between wild-type vs. mutation will use Wilcoxon Rank Sum Test for CL/F of all infants only. The formal comparison will be done only if we have enough infants in the listed genotype groups.

**Table 9: Summary of Infant RAL CL/F between UGT1A1 Genotype Groups for Cohort 2
(mock-up table)**

		UGT1A1 Genotypes					Overall
		Wild-type	Mutation			Overall	
		(TA)6(TA)6	(TA)5(TA)6	(TA)6(TA)7	(TA)7(TA)7		
CL/F from the 1st intensive PK analysis	N						
	mean						
	median						
	...						
CL/F from the 2nd intensive PK analysis	N						
	mean						
	median						
	...						

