Note: This table is for Cohort 2 RAL-naïve group only and should we have data on Cohort 2 RAL-exposed group, additional columns for: (i) RAL-exposed group, and (ii) Overall Cohort 2, will be added. Formal comparisons for all Cohort 2 infants will be done by then.

Table: Association between UGT1A-1 genotypes and hyperbilirubinemia (yes/no) with Fisher’s Exact Test.

Table 10: Summary of Cohort 1 Infant Hyperbilirubinemia between UGT1A1 Genotype Groups (mock-up table)

Characteristic		Wild-type	Mutation				Overall (N=0)	P-value* for all genotype groups	P-value* for Wild-type vs. Mutation
		(TA)6(TA)6	(TA)5(TA)6	(TA)6(TA)7	(TA)7(TA)7	Overall			
Hyperbilirubinemia	Yes	0	0	0	0	0	0.000	0.000	
	No	0	0	0	0	0			

*Fisher’s Exact Test. The power of test will depend upon the distributions of the variables to be analyzed, but will be extremely limited due to the small sample size.
Note: Similar table will be created for Cohort 2 infants.

Table: Association between SLCO1B3 genotypes and hyperbilirubinemia (yes/no) with Fisher’s Exact Test.

Table 11: Summary of Cohort 1 Infant Hyperbilirubinemia among SLCO1B3 Genotype Groups (mock-up table)

Characteristic		C/C (N=0)	C/T (N=0)	T/T (N=0)	Total (N=0)	P-Value*
Hyperbilirubinemia	Yes	0	0	0	0	0.000
	No	0	0	0	0	

*Fisher’s Exact Test. The power of test will depend upon the distributions of the variables to be analyzed, but will be extremely limited due to the small sample size.
Note: Similar table will be created for Cohort 2 infants.

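### SAP 4.9 plans no between-group CL/F ratio or confidence interval for UGT1A1 genotype, and at Cohort 1 numbers the p-values it does plan say little about secondary objective 2.22

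*SAP*

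**What the plan says.** Secondary objective 2.22 of the protocol is to investigate how neonatal raltegravir elimination relates to UGT1A1 genotype. Protocol 8.711 keeps this descriptive: "Descriptive analyses will be performed to compare these subgroups with respect to measures of central tendency and dispersion for raltegravir AUC".

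SAP 4.9 uses CL/F as the elimination measure. Within genotype groups it plans: "Summary descriptive statistics (N, geometric mean, median, 25th and 75th percentiles, min, and max) on CL/F will be generated for the subgroups". Table 8, for Cohort 1, adds two p-value columns. Footnote a reads "Comparison of median among different genotypes will use Kruskal–Wallis test for CL/F of all infants only"; footnote b reads "Comparison of median between wild-type vs. mutation will use Wilcoxon Rank Sum Test for CL/F of all infants only". Both carry the condition "The formal comparison will be done only if we have enough infants in the listed genotype groups", with no number attached.

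Table 9, for Cohort 2 RAL-naïve infants, has no p-value column. Its note says that once RAL-exposed infants contribute data, columns will be added: "Formal comparisons for all Cohort 2 infants will be done by then". No test is named. Neither table has a ratio, a difference or an interval between genotype groups.

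The protocol does give a reference effect. Section 1.27, discussing adults, says that *28/*28 individuals "have on average an increase of 40% in raltegravir AUC" compared with wild type.

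**The concern.** The objective asks how elimination differs by genotype. A p-value from a handful of infants does not give the size of a difference or show which sizes the data rule out. If a Table 8 test is not significant, the reader sees two geometric means and a p-value, and cannot tell whether the reference effect has been excluded or was never detectable. If too few infants are judged available, there is no inferential statement at all, and because the threshold has no number, that choice can be made after the genotype split is known.

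The plan treats neighbouring analyses differently. Tables 10 and 11 warn that power is severely limited; Tables 8 and 9 carry no such warning. For the hyperbilirubinemia regression, protocol 8.711 intends to set the size and direction of effects against earlier findings. The safety proportions get 90% confidence intervals. The elimination comparison is the one with a quantified reference value, and it gets neither an effect estimate nor an interval.

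**Working it through.** The documents give no power, sample size or detectable effect for this comparison, so there is no stated figure to reproduce.

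**Inputs from the documents**
- Cohort 1: 15 of 16 infants PK-evaluable (protocol 1.29).
- Cohort 2: 20 as the protocol minimum, up to 26 RAL-naïve accrued (SAP 2) plus a minimum of 8 RAL-exposed (protocol 8.4), so 34. The value 28 is 20 + 8.
- Genotyping is optional (protocol 3.2), so these counts can only fall.
- Reference effect: AUC up 40%. At a fixed dose CL/F = dose/AUC, so the CL/F ratio is 1/1.4 = 0.714 and the log difference is ln 1.4 = 0.336.
- Log-SD, using AUC spread in place of CL/F spread. AUC24 in the first 10 Cohort 2 RAL-naïve infants (protocol 1.29): ln(78.3/18.6)/3.078 = 0.467, where 3.078 is the expected range of 10 standard normal values. AUC12 in the same section: ln(24.5/4.7)/3.078 = 0.54. The 40% CV in Table 4 (4 weeks to under 6 months): sqrt(ln(1 + 0.40²)) = 0.385.

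**Assumptions not in the documents:** two-sided 5% (the SAP states no alpha), log-normal CL/F, the genotype split, and the full reference effect applying to the whole comparison group.

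**Power.** Simulated exact Wilcoxon rank sum test, log CL/F shifted by 0.336:

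| Group sizes | log-SD 0.385 | 0.47 | 0.54 |
|---|---|---|---|
| Cohort 1, 8 vs 7 | 0.29 | 0.21 | 0.17 |
| Cohort 1, 10 vs 5 | 0.27 | 0.20 | 0.15 |
| Cohort 1, 13 vs 2 | 0.14 | 0.10 | 0.09 |
| Cohort 2, 18 vs 2 | 0.17 | 0.13 | 0.11 |
| Cohort 2, 10 vs 10 | 0.40 | 0.31 | 0.22 |
| Cohort 2, 24 vs 4 | 0.30 | 0.21 | 0.17 |
| Cohort 2, 14 vs 14 | 0.58 | 0.43 | 0.33 |
| Cohort 2, 17 vs 17 | 0.66 | 0.49 | 0.40 |

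In Cohort 1 a non-significant result is therefore expected in about 71% to 91% of trials (1 − 0.29 to 1 − 0.09) even with the full effect present. By the normal approximation n = 2(1.96 + 0.84)² SD²/0.336², 80% power needs about 21, 31 or 41 infants per group at the three SDs.

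**Dilution.** The SAP labels the factor "UGT1A-1 genotype (presence or absence of *28/*28 genetic variant", but its mutation group also includes (TA)5(TA)6 and (TA)6(TA)7. If the pooled group carried only a 20% rise in AUC (an assumption), power would be about 0.08 to 0.13 in Cohort 1 (8 vs 7 or 6 vs 9) and 0.13 to 0.26 in Cohort 2 (28 to 34 infants, near-even split).

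**What an interval would show.** Suppose the observed ratio is 0.714. The 90% CI multiplies and divides it by exp(t × SD × sqrt(1/n₁ + 1/n₂)).
- 8 vs 7, SD 0.467: exp(1.771 × 0.467 × sqrt(1/8 + 1/7)) = 1.53, giving 0.47 to 1.10. At SD 0.385 it is 0.50 to 1.02; at 0.54, 0.44 to 1.17.
- 13 vs 2, SD 0.47: 0.38 to 1.34.
- 14 vs 14, SD 0.47: 0.53 to 0.97.

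The two Cohort 1 examples contain both 0.71 and 1, so they show openly that neither is excluded. The 14 vs 14 example excludes 1.

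**Where the interval stops working.** At 14 vs 1 the most extreme rank has tail probability 1/15 = 0.067, above 0.05, so an exact rank-based 90% interval is unbounded. A minimum group size is still needed.

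**The case against.** The strongest defence is that the plan already does what protocol 8.711 asks. It tabulates central tendency and spread by genotype, including geometric means, so a reader can divide two of them and obtain a crude ratio. A reader might infer that the comparison has been reduced to p-values; the tables do not support that. What is missing is the ratio's precision.

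A reader might also infer that a non-significant result is expected in both cohorts. That is firm only for Cohort 1. Table 9 plans no test for RAL-naïve infants alone, and for the whole cohort power passes 50% in the favourable cases.

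Nor is the 40% figure a prediction for this contrast. It is an adult *28/*28 result, the SAP pools other genotypes with the homozygote, and protocol 3.2 says the effect of these polymorphisms in the first weeks of life is unknown.

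Finally, nothing in the documents says a non-significant test would be reported as no relationship, and the Table 8 footnotes restrict testing to adequate numbers. These points stand. They narrow the concern but do not supply the missing ratio and interval, and adequate numbers remain undefined.

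**Conclusion.** The point holds in a limited form. SAP 4.9 has no between-group effect estimate or interval for CL/F, and for Cohort 1 its planned p-values have power of only about 0.09 to 0.29 against a ratio of 0.71. For all of Cohort 2 the range is about 0.17 to 0.66 with 28 to 34 infants and at least four in the smaller group, and about 0.11 at the worst case run (18 vs 2). These figures rest on the assumed alpha, the assumed genotype splits, AUC spread from few infants, and an adult effect used as a yardstick.

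It would go too far to say an interval cures the low power: the numbers and variability are unchanged, and the gain is that the uncertainty is visible. This is a secondary analysis and the documents tie no dosing or stopping rule to it. It is a cheap improvement, not a flaw in the trial's main conclusions.

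**What to change.** In Table 8, and in the whole-cohort comparison to be added to Table 9 (for each of its two intensive PK occasions), report the geometric mean ratio of CL/F with a two-sided 90% CI from a t interval on log CL/F. Give it for (TA)7(TA)7 versus wild type and for pooled mutation versus wild type. The 90% level matches the safety analyses.

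Replace the undefined sufficiency condition with a stated minimum, for example at least 2 infants in each group. Below it, list individual values.

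If p-values are kept, name the Cohort 2 test, label all of them exploratory, and add the limited-power note already used under Tables 10 and 11. Compare with 0.71 only for the (TA)7(TA)7 contrast, taking that genotype to be *28/*28 and the adult ratio as a benchmark, not a neonatal prediction.

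The cost is revised table shells and a few lines of code on data already planned for collection. The downside is that the intervals will be wide, especially with two or three infants in a group.

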- interim and full cohort accrual safety reports: at full accrual to Cohort 1, at interim analysis when 8 participants have been accrued to Cohort 2 (safety analysis only) and at full accrual to Cohort 2 RAL-naïve group; and
- SDAC final reports: the first report will focus on Cohort 1 (both RAL naïve and exposed groups) and Cohort 2 RAL naïve group. Should protocol Version 2.0 be approved and Cohort 2 RAL-exposed group be opened to accrual, a second report will be generated at study closure to follow-up for Cohort 2 (both RAL naïve and exposed groups).

When applicable, separate summary tables will be generated for the women and their infants. Separate summary tables will be generated for each cohort since Cohort 1 neonates will receive two single RAL dosing while Cohort 2 neonates will receive daily RAL dosing through 6 weeks of life. Summary statistics for subgroups of infants will be provided alongside the overall cohort summary statistics. Infant subgroups will be defined in terms of infant in utero RAL exposure and RAL dosing. For Cohort 1, there are 3 infant subgroups: (i) RAL-naïve (3mg/kg-3mg/kg), (ii) RAL-naïve (2mg/kg-3mg/kg), and (iii) RAL-exposed (1.5mg/kg-3mg/kg). Cohort 2 RAL-naïve group only has one dosing which was specified in **Section 2**.

The interim and full cohort accrual safety reports will be prepared for the core team and, if necessary, for the SMC. These reports will include information concerning Screening and Entry, Participant and Study Status, Baseline, and Safety summary tables. Unless otherwise noted the SDAC final reports will contain all summary tables.

Additional participant listings necessary in writing up the SDAC final report will be generated and will be used internally at SDAC. Highlights of these listings will be included in the SDAC final report. These participant listings will be provided to the manuscript writing team. The manuscript writing team, which is a subset of the protocol team, will be identified by the protocol team.

The analysis of the PK data will be performed by the protocol pharmacologists and thus, not included in this document.

Validation requirements as per SDAC SOPs will be as follows:

- a. All dataset creation programs will be validated with double coding for the primary and secondary safety endpoints.
- b. All study-specific formats will be validated.
- c. Validation of analysis programs is specified in the following subsections.

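### SAP 4.9 tests genotype against hyperbilirubinemia cohort by cohort and silently omits the protocol's conditional pooled model, so secondary objective 2.22 gets no combined estimate

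*SAP*

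**What the plan says.** Secondary objective 2.22 asks whether UGT1A1 (*28/*28) and SLCO1B3 (rs2117032) are associated with hyperbilirubinemia. It does not divide the question by cohort.

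Protocol 8.711 answers it in two steps. The first is descriptive: "Similar descriptive analyses will also be performed to investigate the association of UGT1A1" and SLCO1B3 with hyperbilirubinemia, with nothing said about pooling. The second is conditional: "If the sample size and the data distributions make this possible, a logistic regression model" with both genotypes, gestational age and gender as predictors "will be fitted on the pooled data across the two cohorts". The protocol expects minimal power and possibly too few cases. It says the size and direction of effects will be compared with earlier findings.

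SAP 4.9 lists a table headed "Association between UGT1A-1 genotypes and hyperbilirubinemia (yes/no) with" Fisher's exact test, and the same for SLCO1B3. The mock-ups (Tables 10 and 11) are for Cohort 1, and each carries the note "Similar table will be created for Cohort 2 infants". The footnotes concede that power "will be extremely limited due to the small sample size". No pooled table, stratified test, regression model or odds ratio is listed. The general reason for splitting is in SAP section 4: "Separate summary tables will be generated for each cohort since Cohort 1 neonates will receive two single RAL dosing", while Cohort 2 is dosed daily through 6 weeks.

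SAP sections 4 and 4.6 also split the reporting. The first final report covers Cohort 1 and the Cohort 2 RAL-naïve group. The second covers Cohort 2 only.

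**The concern.** One question receives two unconnected p-values per comparison from very small samples, and no estimate that combines them. The protocol's only cross-cohort analysis of this question is absent from the SAP, with neither a reason nor a fallback for the sparse data that the protocol itself expects. Because no final report contains all four study groups, a reader could not obtain a combined result from the planned output.

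The two p-values can also point in different directions with no rule for reading them together. The protocol values the size and direction of effects, and Fisher p-values alone supply neither. At stake is the interpretability of an exploratory secondary objective. No dose, safety rule or primary endpoint depends on it.

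**Working it through.** **Inputs from the documents.** Cohort 1 has 16 infants (10 + 6) and the Cohort 2 RAL-naïve group has 26 (SAP section 2). The Cohort 2 RAL-exposed group will have at least 8 (Protocol 8.4). Cohort 2 is therefore about 26 + 8 = 34 and the total about 50. Cohort 1 is 16/42 = 38% of infants at the first report and 16/50 = 32% at the end. Genotyping is optional (Protocol 3.2), so these counts are upper limits.

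**Assumptions.** Neither document states an event rate, carrier frequency, effect size, alpha or sidedness for this analysis, so there is no plan figure to reproduce. I assumed a two-sided 5% level, the same effect in both cohorts, a two-group genotype and all 50 infants genotyped.

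**Tests compared.** Within a cohort of N infants with m carriers and e events, Fisher's test refers the number of events in carriers to a hypergeometric (N, e, m) distribution. The stratified exact test refers the sum of carrier events over the two cohorts to the convolution of the two hypergeometric distributions. It compares genotypes only within a cohort, so a different background rate under different dosing cannot bias it.

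**Power, number of carriers random** (simulation, 16 + 34; repeat runs agree to about 0.01):

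| Rates (wild-type vs carrier) | Carriers | Cohort 2 alone | Either cohort p ≤ 0.05 | Stratified |
|---|---|---|---|---|
| 10% vs 50% | 50% | 0.65 | 0.74 | 0.85 |
| 15% vs 40% | 50% | 0.28 | 0.35 | 0.44 |
| 5% vs 20% | 50% | 0.14 | 0.16 | 0.25 |
| 5% vs 20% | 20% | 0.16 | 0.20 | 0.24 |
| 2% vs 10% | 20% | 0.07 | 0.08 | 0.11 |

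In the first row, exactly one of the two cohorts is significant in about 57% of simulated trials.

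**Power, number of carriers fixed at 40%** (exact enumeration; 6 of 16 and 14 of 34):

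| Rates | Cohort 1 | Cohort 2 | Either | Stratified |
|---|---|---|---|---|
| 5% vs 20% | 0.07 | 0.13 | 0.19 | 0.31 |
| 5% vs 30% | 0.18 | 0.36 | 0.47 | 0.64 |
| 10% vs 40% | 0.24 | 0.44 | 0.57 | 0.67 |
| 20% vs 50% | 0.20 | 0.38 | 0.51 | 0.55 |

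Over 21 enumerated non-null scenarios (carriers 20%, 40% or 50%), the stratified test gains 7 to 29 percentage points over Cohort 2 alone and 3 to 17 over significance in either cohort. On first-report data (16 + 26), at 5% vs 30% with 40% carriers, power rises from 0.34 for Cohort 2 alone to 0.52.

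**Size.** The stratified test stays conservative: at most 0.017 at a 5% event rate and about 0.03 at 20%.

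**Floor with few events.** At 40% carriers and 3 events, all in carriers, the smallest attainable p-values are:
- pooled without strata: (20·19·18)/(50·49·48) = 0.058
- all three in Cohort 2: (14·13·12)/(34·33·32) = 0.061
- one in Cohort 1, two in Cohort 2: (6/16)·(14·13)/(34·33) = 0.061
- two in Cohort 1, one in Cohort 2: (6·5)/(16·15)·(14/34) = 0.051
- all three in Cohort 1: (6·5·4)/(16·15·14) = 0.036, which is the Cohort 1 Fisher result itself

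Stratifying therefore adds nothing here, and nothing at 50% carriers either. The floor depends on carriage. At 20% carriers (3 of 16 and 7 of 34), one event in each cohort, both in carriers, gives (3/16)·(7/34) = 0.039 stratified. Neither cohort alone could reach 0.05 on that outcome (0.19 and 0.21).

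**The case against.** **Pooling is not a general protocol requirement.** A reader might infer that the protocol requires pooled data for the genotype association and that the SAP contradicts it. The text does not support that. Pooling attaches only to a logistic regression that is itself conditional, and the Fisher tables correspond to the descriptive step, for which pooling is not stated. The SAP (V3.0, January 3, 2017) also predates protocol Version 2.0 (18 January 2017) and describes that version as still being drafted. What stands is that the model appears nowhere in the SAP and no reason is given.

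**The loss may be small.** A reader might also infer that splitting discards most of the power. That cannot be derived from the documents. The large gains need high event rates. Low rates are plausible: infants above phototherapy thresholds are excluded at entry (Protocol 4.41), and SAP 4.9 counts only bilirubin above 16.0 mg/dL or exchange transfusion, whereas Protocol 8.24 also counts phototherapy and other therapies. At low rates the stratified test is still badly underpowered, as both documents already admit. This stands, and it limits the size of the point.

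**The cohorts are dosed differently.** This is a sound reason for separate descriptive tables. Stratifying deals with different background rates, but it still assumes the same genotype effect under both regimens. Per-cohort tables of this size can check that only weakly.

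**It is an exploratory secondary objective** in a non-comparative Phase I study. This is true, and it argues for a light remedy.

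**Conclusion.** The point holds in a limited form. SAP 4.9 omits the protocol's conditional pooled model without comment and plans no combined test or estimate for objective 2.22. A cohort-stratified exact test had more power than Cohort 2 alone in every non-null scenario tried. The size of the gain rests on assumed event rates, carriage and complete genotyping: from about 0.65 to 0.85 in a favourable case, and from 0.16 to 0.24 in a less favourable one. With 3 or fewer events and 40% or more carriers, there is none. A cohort with no events contributes nothing to a conditional test, so the analysis uses all genotyped infants in informative strata, not all infants enrolled. The calculations cover a two-group genotype. No gain has been shown for the three-group SLCO1B3 comparison.

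**What to change.** In SAP 4.9:

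1. Keep Tables 10 and 11 and their Cohort 2 counterparts as description.
2. Add one exact conditional test per gene, stratified by cohort, over all genotyped infants, and state alpha and sidedness. For UGT1A1, use the SAP's wild-type vs mutation split with an exact common odds ratio and confidence interval. For SLCO1B3, which has three genotypes, fix the coding in advance (for example an exact trend test on the number of C alleles) or use an exact stratified three-group test.
3. State that Cohort 1 genotype and hyperbilirubinemia data are brought into the second final report for this test.
4. Do not let cell counts decide whether in utero RAL exposure becomes a stratum. Protocol 8.3 names it as an analysis stratification factor, so any use of it here must be settled in the SAP beforehand.
5. Say whether the conditional logistic model of Protocol 8.711 is retained, replaced by this test, or dropped, and why.

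The cost is a few SAP lines, a wider scope for the second report and standard exact software, with no new data or blood draws. The price in assumptions is a common genotype effect across the two dosing regimens, which should be stated beside the result.
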